5.7 Duration of Follow-up

For this protocol, all patients, including those who discontinue protocol therapy early, will be followed for response until progression, even if non-protocol therapy is initiated, and for survival for 5 years from the date of registration.

6. Measurement of Effect

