Blood and saliva biomarkers ⁸		X	X	X	X
IMRT					
Nivolumab ^{5,6}		X	X		

¹Pre-study laboratory assessments should be done ≤ 4 weeks before registration.

²Disease evaluation by clinical methods and a CT and/or MRI to assess all measurable or non-measurable sites of disease will be obtained at screening (≤ 4 weeks before registration), symptomatically during IMRT, every 3 months during adjuvant nivolumab treatment starting from end of radiation therapy, every 6 months for 3 years, and annually for 2 more years to confirm standard of care assessments.

³SLP = speech language pathologist; MBS = modified barium swallow; Required for participation at screening and 6 and 24 months after treatment, and if MBS is performed as standard of care.

⁴All labs may be completed within 7 days of surgery.

⁵Nivolumab 240mg IV every two weeks

⁶Nivolumab 480mg every 4 weeks for 6 doses.

⁷TSH to be drawn for baseline status. Is not an eligibility criterion

⁸Blood biomarkers will be drawn at screening, week 0: Day -3 (± 2 Days), every 4 Weeks (post Week 4) x 24 Weeks (± 7 Days), EOT. For LTFU: Every 3 Months x 24 Months then every 6 Months x 3-5 Years from completion of radiation therapy

- a. Serum Cytokines/Chemokines
- b. HPV DNA (blood & saliva)
- c. Tumor antigen specific cellular immunity
- d. Lymphocyte Markers

⁹QOL's will be collected for LTFU at 3, 6, 12, 24 months from completion of radiation therapy

¹⁰ EOT should coincide with 6 month CT scan post radiation therapy.

8. Nivolumab Formulation and Procurement

Product Description / Class and Dosage Form	Potency	IP/Non-IMP	Blinding	Packaging	Storage Conditions (per label)
BMS-936558-01 (Nivolumab) Solution for Injection*	100 mg (10 mg/mL)	IP	Open Label	10 mL per vial (5 or 10 vials/carton)	Store at 2° - 8 °C. Protect from light and freezing.

*May be labeled as either "BMS-936558-01" or "Nivolumab"

Investigational Product

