9.1 Objectives

The dual primary objectives of this phase II study are (1) test the hypothesis that the proposed adjuvant de-escalation strategy (TORS + 50Gy RT + Nivolumab cancer) has equivalent (non-inferior) 2-year PFS. PFS is survival without local, regional or distant disease progression; patients who do not progress or die while disease – free will be censored and (2) to demonstrate a reduction in the rate of PEG tube dependence at one year.

Secondary objectives include estimating recurrence patterns, assessing quality of life (QOL) and swallowing function before and after treatment and evaluating toxicity.

With improved outcomes for p16+ oropharyngeal cancers treatment de-escalation is a critical and topical subject for a controlled clinical. This trial tests the hypothesis that de-escalating treatment of intermediate risk p16+ oropharyngeal cancer patients benefits them by providing equivalent oncologic outcome with superior quality of life.

The first hypothesis to be tested is that oncologic outcome following de-escalation is clinically equivalent to conventional standard systemic therapy with transoral robotic surgery (TORS) plus adjuvant cisplatin and 60-66 Gy radiation. The definition of non-inferiority is clearly within a desired clinical window of equivalence, defined as 2-year PFS, not less than 10% lower than expected under standard-of-care. Therefore, the design is to establish the non-inferiority of the experimental therapy (TORS + Nivolumab + 50 Gy radiation). The second hypothesis to be tested is de-escalation is warranted, by virtue of a clinically meaningful improvement in quality of life as measured by reduced G tube patency.

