9.2 Sample Size and Accrual Rate

Approximately 135 eligible subjects will be enrolled in this multicenter clinical trial that will be conducted at approximately 25 UPMC sites and up to 5 external sites in North America.

The first primary objective is to demonstrate that TORS with de-escalation RT (50Gy) and Nivolumab is equivalent (not inferior) to the standard of care of chemotherapy + standard 60-66 Gy radiation. The first primary endpoint is probability of progression free survival where an event is any type of disease progression or recurrence (local, regional or distant). In this definition deaths from other cancers, other non-cancer causes or treatment related deaths are censored. The historical control for the study is based part upon the results of Huang ⁹ in which the probability of 3 year OS was approximately 65% for high risk (Group III, T4 or N3, age < 70) HPV+ patients treated with chemoradiation and that 3 year OS is an approximation of two year PFS. Since there is not an ideal, published cohort to use, the trial is designed to investigate whether TORS with 50 Gy RT + Nivolumab is not inferior to standard of care chemotherapy + standard 60-66 Gy radiation.

We plan to devote 2 years of accrual and one year of additional follow-up. We assume that the experimental arm is not inferior to the standard if the 2-year PFS is not less than 55%, 10% less than the assumed standard. Thus 55% 2-year TTP for de-escalation RT + Nivolumab is considered not inferior to the 65% 2-year PFS for Cisplatin + 60-66 Gy RT.

Using a one-tailed exponential test (using the maximum likelihood estimator for the hazard rate of the exponential distribution) at $\alpha = .10$, 135 patients will provide 90% power to reject the null hypothesis that the experimental arm is inferior (less than 55% 2-year PFS) when the underlying 2-year PFS is 65%.

The second primary objective is to demonstrate reduction in feeding tube dependence. We will compare 1-year PEG tube dependence for patients who have not progressed to the SOC. Based on

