unpublished results from RTOG 0234 for 84 patients treated with RT + cisplatin + cetuximab, 67 (80%) did not have disease progression at one year. Of these, 11 (16%) were dependent upon a feeding tube one year after the start of treatment. Assuming a 15% PEG tube SOC rate, we wish to demonstrate a 50% improvement or to 7.5% due to the proposed de-escalation regimen. We assume the same 1 year non-progression rate of 80% which suggests 80% of 135 or 108 patients will be candidates for a feeding tube at one year. A one tailed exact binomial test with 108 patients at alpha = .06 will have 80% power to detect a reduction in 1 year PEG tube rate from 15% to 7.5%. Using the Bonferroni inequality, the type I error for testing both primary hypotheses is 16% with 135 patients.

Thus, we require accrual of 45 patients/yr for 3 years (135 total) with one year of additional follow-up.

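### Section 9.2 tests a 2-year PFS hypothesis with an exponential test on all follow-up, so the stated 10% type I error holds only if the hazard is constant throughout

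*Combined protocol and SAP*

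**What the plan says.** Section 9.1 states the first hypothesis as showing that the regimen "has equivalent (non-inferior) 2-year PFS". Section 9.2 sets the limit at 55%, ten points below an assumed standard of 65%, and names one test for it: "Using a one-tailed exponential test (using the maximum likelihood estimator for the hazard rate of the exponential distribution", one-sided at 0.10. It adds that "135 patients will provide 90% power to reject the null hypothesis that the experimental arm is inferior (less than 55% 2-year PFS". The alternative used for that power is a true value of 65%. The 0.10 is then added to the 0.06 for the PEG endpoint, so that "the type I error for testing both primary hypotheses is 16% with 135 patients".

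Follow-up for progression does not stop at 24 months. Section 5.7 follows patients for response until progression and "for survival for 5 years from the date of registration". Section 7, footnote 2, continues imaging "every 6 months for 3 years, and annually for 2 more years". Deaths without progression are censored. Sections 9.1 and 9.2 give no cut of the data at 24 months, no assumed hazard shape, no check of constant hazard and no Kaplan-Meier test of PFS.

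Section 9.2 also gives two timelines: 2 years of accrual plus 1 year (2+1) in the text on the first endpoint, and 3 years plus 1 year (3+1) in its last sentence.

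**The concern.** The hypothesis concerns one point on the curve. The test estimates one average rate over everything observed, up to 4 years per patient at 3+1. The two agree only if the hazard is constant. If few events occur after year 2, that person-time lowers the fitted rate and raises the implied 2-year PFS, even when the true value is exactly 55%. In a de-escalation trial that error runs towards calling an inferior regimen non-inferior. If the hazard falls mostly before year 2 and follow-up is short, the error can run the other way and cost power.

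A constant hazard is a strong assumption here. Under the null it implies 0.55 × 0.55 = 30% progression-free at 4 years. Because deaths without progression are censored, recurrences alone must sustain that rate.

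**Working it through.** **Inputs from 9.2:** n = 135, one-sided alpha 0.10 (z = 1.2816), power 90%, 2-year PFS 55% against 65%, accrual and follow-up 3+1 or 2+1.

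**Hazards.** λ0 = −ln(0.55)/2 = 0.2989 per year; λ1 = −ln(0.65)/2 = 0.2154 per year; ln(λ0/λ1) = 0.3277.

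**Reproducing the stated power.** With uniform accrual over A years and F further years, the event probability is p = 1 − [exp(−λF) − exp(−λ(A+F))]/(λA).

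- At 3+1: p0 = 1 − (0.7416 − 0.3025)/0.8968 = 0.510 (68.9 events); p1 = 1 − (0.8062 − 0.4225)/0.6462 = 0.406 (54.8 events).
- Power = Φ{√54.8 × (0.3277 − 1.2816/√68.9)} = Φ(1.283) = 90.0%.
- N = (1.2816/√p0 + 1.2816/√p1)²/0.3277² = 135.

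The plan's figure is reproduced, but only in this setting:

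- 2+1, all follow-up: power 86.5%; 90% would need 158 patients.
- 3+1, data cut at 24 months: power 85.2%; 90% would need 167.
- 2+1, data cut at 24 months: power 84.2%; 90% would need 173.

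So the 90% relies on person-time after 24 months.

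**Type I error when the hazard is not constant.** Every curve below is an assumption, with PFS at 24 months fixed at exactly 55%. The exponential test rejects when ln(λ̂/λ0) × √D < −1.2816, where D is the number of events and λ̂ is D over person-time. The Kaplan-Meier test compares ln(−ln Ŝ(2)) with ln(−ln 0.55), using Greenwood's variance. Results are from simulation (20,000 to 40,000 trials per setting, progression dated when it occurs).

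| Assumed shape | Exponential, 3+1 | Exponential, 2+1 |
|---|---|---|
| Constant | 9-10% | 9-10% |
| Weibull, shape 0.9 / 0.7 / 0.5 | 10 / 12 / 12% | 8 / 5 / 3% |
| Plateau, S(t) = π + (1−π)exp(−μt), π from 20% to 50% | about 13 to 27% | about 9 to 5% |
| Drop at 12 months, ×0.5 / ×0.25 | 11 / 14% | 5 / 3% |
| Drop at 18 months, ×0.5 / ×0.25 | 18 / 26% | 8 / 7% |
| Flat to 24 months, then ×0.75 / ×0.5 / ×0.25 | 18 / 32 / 49% | 13 / 17 / 22% |

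The Kaplan-Meier test stays at 9-11% under every shape and both timelines.

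**Overall error.** The 16% is 0.10 + 0.06. With 12% for the first test the same sum is 18%; with 32% it is 38%.

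**Power of the Kaplan-Meier test** at true 65% with constant hazard: about 82% at 3+1, 80% at 2+1, and 87% once every patient has 24 months.

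**The case against.** **The large figures need a special curve.** This stands. The values of 32% and 49% require a hazard that is flat to month 24, falls at once to a half or a quarter, and is observed for 3+1 years. A smooth Weibull decline at 3+1 adds only about 2 points, and at 2+1 the test is often conservative. A reader might infer that any falling late hazard inflates the error to a third or a half. The documents give no hazard shape, so they do not support that.

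**The scan schedule says nothing about risk.** This also stands. A reader might take thinning surveillance as the sponsor's own expectation of falling hazard. Footnote 2 ties the schedule to standard of care, and the intervals change after adjuvant nivolumab and again after the 6-monthly phase, not at month 24.

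**Kaplan-Meier has a timing problem of its own.** PFS runs from study entry (6.1), but scans are timed from the end of radiotherapy. Assuming that point is 5 to 8 weeks after entry, the last scan before month 24 falls near month 19 to 20, where true PFS under a constant-hazard null is about 61-62%. If progression is seen only on scans, simulated type I error without a window is about 50-60% for Kaplan-Meier and 44% for the exponential test at 3+1. Clinically detected recurrences would reduce both. This affects both tests. It calls for an assessment window and does not rescue the exponential test.

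**The later read-out costs time.** Section 9.1 promises a result 3 years from first accrual and gives a five-year delay as a reason not to randomize. Waiting until every patient has 24 months means 5 years at 3+2. That cost is real, although 3+1 already exceeds the promise.

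**Conclusion.** The point holds in a conditional form. Hypothesis and test do not match, the stated power depends on follow-up after 24 months, and the 10% error (with the 16% overall) is guaranteed only under a constant hazard, which the plan neither states nor checks. With true 2-year PFS of 55% and 135 patients, the error over the assumed shapes is about 10-49% at 3+1 and about 3-22% at 2+1. No single value in those ranges can be called the trial's actual type I error, since the answer depends on a hazard shape and a timeline that the documents leave open. What can be said is that the Kaplan-Meier test keeps close to 10% under every shape tried when progression is dated as it occurs, and the exponential test does not.

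**What to change.** In 9.2:

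1. Make the primary test the Kaplan-Meier 24-month PFS: non-inferiority if the one-sided 90% lower bound on the log-minus-log scale exceeds 55%. Kaplan-Meier estimation is already planned in 9.3 for recurrence and overall survival.
2. Define an assessment window so that the scan nominally due at 24 months counts, and say how progression found in it is dated.
3. Keep the exponential test as a supportive analysis.
4. Restate power as about 82% at the 3+1 cut-off (about 80% at 2+1), or about 87% if the analysis waits until every patient has 24 months.
5. Reconcile the 2-year and 3-year accrual statements, and the 3-year read-out in 9.1.

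**Cost.** About 8 points of stated power if the 3+1 date is kept, or about 3 points and a read-out 12 months later. No extra patients or scans. These power figures assume progression is dated when it occurs, so they should be recomputed once the window is set. In the extreme case where every progression is found only on a scan, with the 5 to 8 weeks assumed above, counting the 24-month scan makes the test conservative (type I error about 4%, power about 67% at 3+1).

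### The PEG co-primary is tested only in patients progression-free at one year and can succeed alone, so a tube reduction could be declared with no larger share of all patients progression-free and tube-free than in the cited cohort

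*Combined protocol and SAP*

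**What the plan says.** Sections 2.1 and 9.1 give the second primary objective as a lower rate of PEG dependence at one year, with no restriction on who is counted. Section 9.1 then treats a gain on this endpoint as what justifies de-escalation.

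Section 9.2 narrows the analysis set: "We will compare 1-year PEG tube dependence for patients who have not progressed to the SOC". The benchmark is "unpublished results from RTOG 0234 for 84 patients treated with RT + cisplatin + cetuximab", of whom "67 (80%) did not have disease progression at one year. Of these, 11 (16%) were dependent upon a feeding tube". The plan rounds this to a fixed null: "Assuming a 15% PEG tube SOC rate, we wish to demonstrate a 50% improvement or to 7.5" (per cent). It assumes that "80% of 135 or 108 patients will be candidates for a feeding tube at one year", and states: "A one tailed exact binomial test with 108 patients at alpha = .06 will have 80% power". The two co-primaries receive one-sided alphas of 0.10 (PFS) and 0.06 (PEG), added by Bonferroni to 0.16.

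No analysis of PEG dependence in all patients is planned, and no rule says that both co-primaries must succeed. The data would allow an all-patient analysis: section 9.6 tracks feeding-tube status at every PRO time point, section 5.5 includes a 12-month time point, and it continues QOL collection after recurrence.

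**The concern.** Whether a patient enters the PEG denominator depends on an outcome that the reduced radiation dose and the omission of cisplatin could affect. A patient who progresses leaves the denominator, along with any tube placed after recurrence. If progression is more frequent than in the benchmark cohort, the tube rate among the remaining patients can fall while the share of all patients who are free of both progression and a tube does not rise.

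This matters because the alpha split lets PEG success stand as a claim of its own, and section 9.1 ties the case for de-escalation to that result. A reader of a positive PEG result would naturally take it to describe everyone treated.

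**Working it through.** **Inputs (section 9.2).** N = 135; PEG null 15%, alternative 7.5%; one-sided exact binomial test at alpha 0.06; 80% non-progression at one year, giving 108 evaluable; benchmark cohort of 84 treated, 67 non-progressors, 11 with a tube; PFS boundary 55% and assumed standard 65% at two years, exponential model.

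**1. The plan's own figure.** With X ~ Binomial(108, p), reject when X ≤ c.
- c = 10: P(X ≤ 10 | 0.15) = 0.0559 and P(X ≤ 10 | 0.075) = 0.814.
- c = 11: size 0.0984, too large.

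The stated 80% power at alpha 0.06 is reproduced.

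**2. All-patient share in the cited cohort.** (67 − 11)/84 = 56/84 = 66.7%, exact 95% CI 55.5% to 76.6%. Scaled to 135 patients, this is 90.

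**3. Can the test succeed without exceeding that share?** Recompute the exact cut-off for m evaluable patients.

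| Evaluable m | Tubes | Exact p against 15% | Progression-free and tube-free |
|---|---|---|---|
| 108 | 10 | 0.0559 | 98/135 = 72.6% |
| 105 | 9 | 0.037 | 96/135 = 71.1% |
| 99 | 9 | 0.0595 | 90/135 = 66.7% |
| 95 | 8 | 0.042 | 87/135 = 64.4% |

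All four are PEG successes. The third equals the cited cohort and the fourth is below it.

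**4. How often?** Under the exponential model, one-year PFS is S(1) = √S(2). Let m ~ Binomial(135, S(1)), tubes k ~ Binomial(m, 0.075), and c(m) be the exact cut-off. Sum the probabilities over k ≤ c(m) for PEG success, and over k ≤ c(m) with m − k < 90 for success with a share below 66.7%.

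| True 2-year PFS | One-year PFS | Expected m | PEG success | PEG success with share below 66.7% |
|---|---|---|---|---|
| 55% | 74.2% | 100.1 | 74% | 13% |
| 60% | 77.5% | 104.6 | 76% | 3% |
| 65% | 80.6% | 108.8 | 77% | 0.3% |

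**5. If both co-primaries must succeed.** Both tests were simulated together: exponential PFS, uniform accrual plus one year of follow-up, a Wald test on the log hazard, and a PEG rate of 7.5%. At a true 2-year PFS of 55%, PFS succeeds in about 9% of trials and both tests in about 7%. Both succeeding with the share below 66.7% occurs in under 0.1% of trials at 55%, 60% and 65%. Two-year and three-year accrual (section 9.2 mentions both) give similar results.

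**The case against.** **The conditioning is deliberate and like for like.** The benchmark is also restricted to non-progressors, and a tube placed for recurrence is not a measure of late treatment toxicity. This stands. A reader might infer that the PEG test is invalid or its power misstated; the documents do not support that. The test answers a question about non-progressors, and the arithmetic is right.

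**Progression is the other co-primary.** Section 9.1 describes the aim jointly, as equivalent oncologic outcome together with better quality of life. So a reader who infers that the plan hides progression goes too far. However, the joint description is not written as a decision rule, and the Bonferroni split is the usual treatment of separate claims. The protection in step 5 is strong but depends on a rule that is not stated.

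**The 55% case is the least favourable one shown.** It is the PFS null boundary, which the PFS test would fail to reject about nine times in ten. The expected all-patient share there is 0.742 × 0.925 = 68.6%, slightly above 66.7%, so a typical trial at the boundary does not fall below the benchmark. This stands, and is why the problem is sized by the 13%, 3% and 0.3% figures together.

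**The cited 56/84 is a weak yardstick.** The results are unpublished and the interval spans 21 points. The plan does not say how deaths without progression or missing tube status were counted. The cohort's year runs from the start of treatment, whereas the trial's 12-month PRO point runs from completion (section 5.5; schedule of assessments, note 9). This stands, and rules out using 66.7% as a pass/fail threshold.

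**An all-patient primary test would be underpowered.** Also correct. With the alternative 0.80 × 0.925 = 74%, power at N = 135 is 46% against a null of 0.80 × 0.85 = 68%, and 61% against 66.7%. Replacing the primary test is not justified.

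**Conclusion.** The concern holds as a gap between the stated objective and the tested population, combined with a missing joint-success rule. It is not an arithmetic error. As written, a PEG reduction can be declared on its own with no larger all-patient share than in the cited cohort. The chance of success with a share below 66.7% is about 13% at a true 2-year PFS of 55%, about 3% at 60%, 0.3% at 65%, and under 0.1% throughout if both co-primaries must succeed.

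These figures assume exponential PFS, a true PEG rate of 7.5% among non-progressors, complete tube status, and no deaths without progression in the first year. PFS in sections 9.1 and 9.2 censors such deaths, and the plan does not say how they enter the PEG denominator. The comparison with 56/84 is descriptive.

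**What to change.** Keep the binomial test, its alpha and the sample size. In sections 9.1 and 9.2:

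- State that the PEG conclusion applies to patients progression-free at one year, and say how deaths without progression and missing tube status are counted.
- State that de-escalation is called justified only if both co-primaries succeed.
- Add a pre-specified supportive estimate in all registered patients: the proportion alive, progression-free and PEG-free at one year, denominator all enrolled, with an exact CI. Report tube status in progressors as well.
- Show this estimate beside 56/84 and its interval (55.5% to 76.6%), descriptively and not as a gate, noting that the one-year clock and the handling of deaths may differ.

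The cost is SAP wording and one further estimate from tube data already tracked; no patients, visits or alpha are added. The downside is a narrower functional claim that is harder to make in full. With the plan's stated powers, and treating the two tests as independent, the chance of both succeeding is 0.90 × 0.80 = 0.72.

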2.1 Primary Objective

The dual primary objectives of the study are (1) to test the hypothesis that the proposed adjuvant de-escalation strategy (TORS + 50Gy RT + Nivolumab cancer) is equivalent (non-inferior) to current standard of care cisplatin chemotherapy + standard 60-66 Gy radiation, and (2) to demonstrate a reduction in the rate of PEG tube dependence at one year.

Primary Hypotheses: We hypothesize that HPV + OPC is a distinct immunologic disease with a more favorable prognosis compared to HPV- OPC and represents a novel opportunity for de-escalation strategies in the adjuvant setting in Intermediate-Risk p16+ OPC groups after trans-oral resection (TORS). Risk-Adaptive de-escalation through a combination of TORS surgical resection followed by de-escalated RT (50 Gy accelerated fractionation) and concurrent Nivolumab immunotherapy in HPV+ OPC patients will result in similar PFS compared to historical results of standard CRT studies (60-66 Gy +/- Cisplatin) in the adjuvant setting, typically recommended for Intermediate and High Risk patients (HPV-, >4 metastatic nodes, + extensive ENE, + margins), as well as improvement in secondary endpoints of reduced toxicity, and patient QOL measures.

We further hypothesize that RT combined with concurrent and adjuvant Nivolumab will offer similar PFS outcomes to historical trials using cisplatin-based CRT through reduced tumor microenvironment immune suppression, enhanced systemic immune activation and response, and reduced toxicity by eliminating standard chemotherapy and allowing de-escalated RT.

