5.5 Supportive care and Other Assessments

Patient Reported Outcomes (PROs)

Quality of Life (QOL) assessments will be performed at baseline, end of treatment, and at 3, 6, 12, and 24 months after completion of treatment. If an additional tumor assessment is done prior to 3 years from study entry, one final QOL assessment is requested. QOL will continue to be collected for all patients post recurrence.

Paper questionnaires will be completed by the patient, and then data from the questionnaire should be provided within 7 days of completion. The original copy needs to be kept in the study subject's research binder.

Rehabilitation

It is strongly encouraged that all patients be referred for an assessment by a certified physical therapist after the completion of concurrent therapy. Components of the evaluation should include: neck shoulder and jaw range of motion, general conditioning level, the degree of treatment related fatigue, and postural issues. Patients with significant levels of deconditioning, postural abnormalities, or decrease in range of motion may require physical therapy. Occupational therapy may be needed in patients with extreme degrees of dysfunction. Patients with lymphedema should be referred for lymphedema therapy which should include: education, manual lymph drainage and the use of compression garments.

Speech and Language Pathology

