9.6 Observer-Assessed Outcomes

Performance Status (PS): Performance status will be assessed using the ECOG performance status scale and must be 0-1 at baseline for study eligibility. Changes in ECOG PS will be tracked at all PRO endpoints.

Weight Loss: The degree of weight loss may contribute to fatigue, weakness and deconditioning. Weight loss during therapy will be documented as well as post-treatment weight changes.

Tracheostomy and Enteral Feeding Tube Status: The presence of either assistive device will be tracked prospectively at all PRO time points.

Charlson Comorbidity Index: Comorbidity will be documented by chart abstraction at baseline.

Head and Neck Cancer Specific Performance Status: The Performance Status Scale (PSS-HN)⁶⁸ is a clinician-rated instrument consisting of 3 questions: normalcy of diet, public eating, and understandability of speech. The PSS-HN has been psychometrically validated and recommended by the National Comprehensive Cancer Network for measurement of swallowing and speech

performance in patients with head and neck cancer. It is not a PRO; it can be completed quickly by the trialist without adding to patient burden.

Swallowing Endpoint: Swallowing outcomes will be measured as a secondary endpoint of this trial using modified barium swallow (MBS) studies according to the assessment schedule. A standardized contrast medium (Varibar® thin liquid and pudding contrast, Bracco Diagnostics, Inc. Princeton, NJ) and digitally record MBS studies (30 frames/second) must be used. Three swallowing outcomes will be rated by the SLP conducting the MBS study and reported by research staff: 1) laryngeal penetration (yes, no); 2) aspiration (no, sensate, silent), and 3) pharyngeal residue (no, < 50%, > 50%). These have been selected as universal items generally reported by swallowing clinicians that have been shown to significantly predict pneumonia in patients with oropharyngeal cancers. Prevalence of these dysphagia endpoints will be estimated at each time point.

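### A positive one-year PEG test shows a rate below 15%, not by itself a reduction from standard of care, and the trial's one-year clock is undefined

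*Combined protocol and SAP*

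**What the plan says.** The second co-primary objective (Sections 2.1 and 9.1) is "to demonstrate a reduction in the rate of PEG tube dependence at one year". Section 2.1 gives the comparator as "current standard of care cisplatin chemotherapy + standard 60-66 Gy radiation". Section 9.2 states the comparison as "We will compare 1-year PEG tube dependence for patients who have not progressed to the SOC".

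The benchmark comes from "unpublished results from RTOG 0234 for 84 patients treated with RT + cisplatin + cetuximab". Of these, 67 (80%) were free of progression at one year, and 11 of the 67 (16%) were "dependent upon a feeding tube one year after the start of treatment". The plan then writes: "Assuming a 15% PEG tube SOC rate, we wish to demonstrate a 50% improvement or to 7.5% due to the proposed de-escalation regimen". It specifies a one-tailed exact binomial test with 108 patients (80% of 135), alpha 0.06 and 80% power.

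On data collection, Section 9.6 says of tracheostomy and feeding tubes: "The presence of either assistive device will be tracked prospectively at all PRO time points". Section 5.5 times the follow-up PRO visits "at 3, 6, 12, and 24 months after completion of treatment". Section 7, footnote 9, counts the same months from completion of radiotherapy instead.

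**The concern.** There are two gaps between the test and the claim it is meant to carry.

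First, the 15% is labelled the standard-of-care rate, but the cohort behind it received cetuximab as well as cisplatin and radiotherapy. No section says why that cohort stands in for cisplatin with 60-66 Gy. The test also treats the rate as known, although it rests on 67 patients. The 6% error rate belongs to the statement that the rate is below 15%. It carries over to a reduction from standard of care only if the standard's rate is about 15% or higher.

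Second, the benchmark is counted from the start of treatment. The trial's own one-year endpoint has no stated origin, and the visits that record tube status use two other origins. Two sites could each follow the protocol and record status at different times, neither matching the benchmark.

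At stake is the wording of a co-primary conclusion: that de-escalation reduces feeding-tube dependence.

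**Working it through.** **1. Reproduce the plan's figure.** Inputs from Section 9.2: n = 0.80 × 135 = 108, null 15%, alternative 7.5%, one-sided alpha 0.06. With X the number of patients with a tube, X ~ Binomial(108, p):

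- P(X ≤ 10 | 15%) = 0.0559 and P(X ≤ 11 | 15%) = 0.0984, so the rule is to reject at 10 or fewer.
- Power: P(X ≤ 10 | 7.5%) = 0.8135.

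The stated 80% power is reproduced.

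**2. What rejection shows.** At the boundary, 10/108 = 9.3%, the one-sided 94% upper bound is 14.9%. At 9/108 it is 13.8%. Rejection therefore excludes 15% and little beyond it. The two-sided exact 95% CI reaches 16.4% at 10/108 and 15.2% at 9/108, so it can appear to contradict a positive test.

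**3. Precision of the benchmark.** 11/67 = 16.4%, with Clopper-Pearson 95% CI 8.5% to 27.5%.

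**4. False-positive rate if the standard's true rate is s.** If the regimen gives no reduction, its own rate is also s, and the chance of declaring success is P(X ≤ 10 | 108, s). The values of s below are assumptions inside the source interval:

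| s | P(X ≤ 10) |
|---|---|
| 12% | 0.239 |
| 14% | 0.095 |
| 15% | 0.056 |
| 16.4% | 0.024 |
| 20% | 0.002 |

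**5. Weight on those values.** Assume the cohort does represent the standard. A Jeffreys prior, Beta(0.5, 0.5), with 11 events and 56 non-events gives Beta(11.5, 56.5). Then P(s < 15%) = 0.36, P(s < 12%) = 0.13 and P(s < 10%) = 0.05. Averaging P(X ≤ 10 | 108, s) over this distribution gives 0.096, against the planned 0.06. This measures sampling error only. It does not measure the effect of using a different regimen as the benchmark.

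**6. The result expected under the design.** 7.5% of 108 is about 8. For 8/108 (7.4%, exact 95% CI 3.3% to 14.1%), P(X ≤ 8) is 0.013 at 15%, 0.087 at 12% and 0.24 at 10%. That result supports a rate below 15%, but not a rate below 12% at the 0.06 level.

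**7. Time origin.** Radiotherapy is 25 fractions at 6 per week (Section 5.1), which the schema describes as four weeks plus one day, or about 29 days.

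- Benchmark: 12 months from the start of treatment.
- Section 7, footnote 9: 365 + 29 = 394 days, about 13 months from the start of radiotherapy. The first nivolumab dose is a few days earlier. The ±1 week window in Section 7 does not close this gap.
- Section 5.5, if treatment includes adjuvant nivolumab: six doses every 4 weeks, starting in the second or third week after radiotherapy (Section 5.2), end about 29 + 14 + 5 × 28 = 183 days from the start. Adding 12 months gives about 18 months. If completion is instead the end-of-treatment visit, tied to the 6-month post-radiotherapy scan (Section 7, footnote 10), it is about 1 + 6 + 12 = 19 months.

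**The case against.** Much of this comes with a single-arm design, which Section 9.1 chooses openly and with reasons. Every one-sample test shows only that a rate lies below its null. Section 9.2 labels 15% an assumption and discloses the source, the counts, the regimen and the unpublished status. It rounds down from 16.4%, which is the strict direction: at the source estimate the false-positive rate is 2.4%. It also restricts benchmark and trial alike to patients without progression. On the model in step 5, the null is more likely too strict than too lenient. All of this stands. The absence of a sentence justifying the proxy is missing detail, not an error.

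A reader might infer that cetuximab inflated the benchmark, so that the trial is set up to succeed. The documents do not support that. They do not give the cohort's radiation dose, tumour site or HPV status, and nothing in them shows which way the proxy errs. A reader might also take the 3% (Section 1.2) or 6% to 8% (Section 1.5) tube rates as the true standard. Those come from other regimens and are not restricted to non-progressors. Nor is the 48% false-positive rate at a true standard of 10% a fair headline, since the source data put only about 5% probability below 10%.

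On timing, one can say that the 12-month visit after radiotherapy is operational and only a month late, and that no section shows how much tube dependence changes in that month. That is fair for the 13-month reading. It does not answer the 18 to 19 month reading or the absence of any stated origin. It is also true that the plan does not say what counted as the start of treatment in the benchmark cohort.

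**Conclusion.** The point holds as a matter of interpretation and endpoint definition. The sample size, alpha, power and rejection rule are correct for a test against a fixed 15%. What a positive result supports is one-year tube dependence below 15%. Calling it a reduction from standard of care needs the further assumption that cisplatin with 60-66 Gy has a rate of about 15% or more, which the plan does not show. If the source cohort does represent the standard, the cost of treating its rate as known is modest: about 9.6% average error against 6%. If it does not, the size and the direction are both unknown.

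The clock is the more concrete defect. As written, tube status is collected about one month, or about six to seven months, later than the benchmark's 12 months, depending on which section is followed. The comparison is then not like for like. Neither issue invalidates the trial, but both should be settled before the co-primary result is analysed.

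**What to change.** 1. Keep the 15% test, n, alpha and power. In Section 9.2, state that success means a rate below 15%. Report the observed rate with an exact 95% CI, together with the one-sided 94% upper bound that matches the test. Add a short sensitivity check at a few nulls on both sides of 15% and inside the source interval, for example 10%, 12% and 20%. A sentence on why this cohort was chosen would help.
2. Define the endpoint as tube dependence 12 months from the start of protocol treatment, and use the same date to decide who has not progressed. Record tube placement and removal dates so that status on that day can be derived without an added visit. Reconcile the visit origins in Section 5.5 and Section 7, footnote 9.
3. Section 9.1 names ECOG 3311 Arm D as the trial's comparison, but the plan gives no tube rate from it. If one-year tube data exist for comparable non-progressing patients, use them only as a supportive comparison that carries its own sampling error. Such data may not be available: Section 1.5 describes that trial as not yet closed.

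The cost is some plan wording, a small table and two date fields, with no extra patients. The real downside is a less favourable claim: below 15%, rather than a reduction from standard of care.
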